### 3.5 Inclusion Criteria

Participants/specimens are eligible to be included in the study only if all the following inclusion criteria apply:

- Adult individuals ( $\geq 18$  years of age) with symptoms suggesting plausible COVID-19 infection (as per WHO or national clinical case definitions)
- Individuals who have voluntarily given written consent to participate in this study or who have given their written consent for their specimen to be used for future research studies
- Individuals providing the specimens required for the study.

### 3.6 Exclusion Criteria

Participants are not eligible to be included in the study if any of the following exclusion criteria apply:

- Individuals on oxygen therapy
- Individuals with recent history of excessive nose bleeds
- Individuals with hemodynamic instability as determined by their treating physician
- Individuals already enrolled in other clinical studies, where similar respiratory specimens are collected on the same day.

### 3.7 Screen Failures

Screen failures are defined as participants who verbally consent to participate in the clinical study but are not subsequently entered in the study. A minimal set of information is required to ensure transparent reporting of screen failure participants to meet the Consolidated Standards of Reporting Studies (CONSORT) publishing requirements and to respond to queries from regulatory authorities. Minimal information includes demography, eligibility criteria, screen failure reasons, and any serious adverse event (SAE). Individuals who do not meet the criteria for participation in the study (screen failure) may not be rescreened. Screen failures should not have an assigned participant study ID but should be recorded on the screening log.

## 4 Study Intervention

Study Intervention is defined as any investigational intervention(s), marketed product(s), or medical device(s) intended to be used with a study participant according to the study protocol.

### 4.1 Investigational Product

***Novel molecular POC tests results will not be used for clinical decision making.***

A total of 3 molecular POC devices, detecting SARS-CoV-2 and other viral pathogens, have been selected by FIND through open calls for expressions of interest. These are Nudge test, Mirai test and GenomEra test. These will be evaluated at LSTM (Nudge test), HUG (Mirai test) and CPHL (GenomEra test). The novel molecular POC devices under evaluation within this protocol are also listed in Appendix 1. Other tests, currently in late development stage, may be considered as they become available for clinical performance evaluation and vetted through discussions with FIND and the WHO Collaborating Centre for COVID diagnostic test evaluation.

Instructions for use of the investigational products will be provided by each manufacturer and shared with sites.

Medical device incidents, including those resulting from malfunctions of the device (or IVD), must be detected, documented and reported by the Investigator at each site throughout the study (see Appendix 2).

## 4.2 Preparation/Handling/Storage/Accountability

### Acquisition

Procurement of the investigational products (devices and test kits) will be done through FIND, who coordinates shipments from the manufacturer or FIND warehouse in Geneva, Switzerland, to study site. It is the responsibility of each study site to maintain an updated inventory of the study materials and inform FIND immediately if additional materials are required.

The Investigator or designee must confirm that appropriate temperature conditions have been maintained during transit to the testing sites. In turn, testing sites will maintain an updated inventory of the investigational product received. Any discrepancies must be reported to FIND and resolved before its use.

### Installation and Storage

Procedures for devices installation and test kits storage and disposal will be described in the corresponding Instructions for Use (IFU) and manuals. Device installation will strictly adhere to manufacturers instruction, meeting all manufacturer and site-specific requirements as well for new equipment installation.

The investigational products (devices and test kits) will be installed and stored in a secure, environmentally controlled, and monitored area in accordance with the labelled storage conditions with access limited to the Investigator and authorized site staff.

### Test Handling and Performance

Testing using the investigational products will be performed according to the manufacturer's instructions. Only respiratory samples, as per index test manufacturer's claim, from participants enrolled in the study or from biobanks will be processed with the investigational product for the main aims and only authorized site staff will be responsible for processing.

### Accountability

The Investigator is responsible for study intervention accountability, reconciliation, and record maintenance (i.e., receipt, reconciliation, and final disposition records). Investigational product accountability logs filled at each site will ensure the proper follow-up of the devices and used, failed and remaining test kits.

### Export and Import Permits

The Investigator at study site is responsible for making import permit applications in a timely manner. FIND logistics team will support providing documentation required from the Sponsor, usually including commercial invoice, packaging list and FIND donation letter. (SITE to amend accordingly where necessary.)

### Quality Check for Incoming Shipments

Upon arrival of each new shipment of devices and assays, the sites will conduct an incoming quality check (visual inspection of integrity of device, check expiry date of device-associated kits, visual inspection of integrity of kit components). New lots may only be used after this quality check is successfully passed.

### **Local procurement**

Sites are responsible for assessing their needs and procuring any supplies, reagents and kits needed for the study that are locally available and to include these costs in the study budget prior to the study initiation.

## **4.3 Minimisation of Error and Bias**

### **Participant/specimen selection**

Spectrum bias will be avoided by enrolling a consecutive series of study participants, and by using a prospective study design. Enrolment will be based on clearly defined eligibility criteria. To ensure the validity and generalizability of study results, descriptive statistics on participant characteristics (days since symptom onset and RT-PCR Ct values, as surrogate for viral load) will be reported.

If frozen or same-day fresh left-over specimens will be used, spectrum bias will be avoided by:

- Randomly selecting specimens from biobanks, considering only inclusion criteria and previous RT-PCR qualitative result (positive or negative)
- Testing consecutive fresh left-over specimens from the diagnostic laboratory, considering only the inclusion criteria.

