**(SITE to add specific setting details, where needed)**

Considering that the COVID-19 pandemic situation is constantly changing, and countries are moving from an acute pandemic response towards coexistence with the virus, supplementing approaches to meet the study objectives may be discussed with single study sites and adopted during the study, provided that specific go/no go criteria are met, and study validity and integrity can be preserved. Potential supplementing approaches considered:

1. Enrichment strategies for recruitment may be considered in case of low prevalence of COVID-19 in the evaluation settings, e.g., including close symptomatic contacts of a confirmed COVID-19 cases through contact tracing procedures.
2. Should the local COVID-19 epidemic situation and/or country-specific policies (e.g., COVID-19 related restrictions, testing centres and recommendations, etc) change in any of the selected countries, making difficult to continue with the prospective study design and to achieve study objectives, frozen respiratory specimens from FIND or local biobanks and/or same-day, fresh respiratory specimens left-overs available in the local diagnostic laboratory may be used. This is in accordance with WHO guidelines for conducting NAT test evaluations (PQDx\_347 COVID-19 NAT and Ag RDTs version 6; 17 March 2022 (who.int))
3. Additional sites may be considered should the COVID-19 pandemic situation change in the above-mentioned sites, making the study no longer feasible.

Supplemental procedures will allow to achieve the primary objective of the study and, most likely, to assess the usability of the POC under evaluation. Data collected, though, may not be sufficient/available to perform the subgroups analyses of the secondary objectives.

Clinical performance of molecular POC devices for viral pathogens other than SARS-CoV-2 included in their detection panel will not be evaluated. Specificity, sensitivity of each index test will be evaluated against WHO/FDA EUL-approved RT-PCR test as a reference method, as recommended by the WHO guidelines.

All study specimens and relevant information will be collected from enrolled participants on the day of recruitment. There will be no follow-up visits. Only PCR results can be communicated to the participant.

Additional sites may be considered should other POC devices pass FIND's screening for clinical performance evaluation.

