## 6 Study Procedures

Study procedures and their timing are summarized in the Schedule of Activities. Protocol waivers or exemptions are not allowed.

Adherence to the study design requirements is essential and required for study conduct.

All screening evaluations must be completed and reviewed to confirm that potential participants/specimens meet eligibility criteria. The investigator will maintain a screening log to record details of all participants screened and to confirm eligibility or record reasons for screening failure, as applicable.

Detailed study procedures will be described in the Study Manual.

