Participants will be diagnosed based on RT-PCR results performed on the routine diagnostic sample (nasopharyngeal swab) and clinical signs and symptoms by their treating physician; results of novel molecular POC devices tests will not be used for clinical management.

**Table 2:** Sample types and testing

Sample Type	Testing	Additional Notes
Routine RT-PCR Nasopharyngeal Swab (x1)	
 
Molecular reference testing for COVID-19 (RT-PCR) as per standard of care (usually placed in standard VTM/UTM).
 
Mirai device testing for study purposes (processed as recommended by test manufacturer in the IFU).
 
	Transported at 2-8°C to reference/testing laboratory after collection. Leftover sample after RT-PCR testing will be kept at -70°C or lower until the study ends or longer depending on the site-specific informed consent. Leftover samples may be used for repeating RT-PCR testing and/or genomic sequencing following positive RT-PCR results. SITE to clarify whether the remaining specimen may be stored in biobank for future studies.
Molecular POC devices specific respiratory sample: 
 
Nasal Swab for Nudge and GenomEra (x1 as per assay IFU);
 
Nasopharyngeal Swab for Mirai (the same sample for reference test can be used)
 
	Nudge, Mirai and GenomEra devices testing for study purposes (processed as recommended by test manufacturer in the IFU).	Processed immediately (within 3h max from collection or as per instructions agreed with the specific device manufacturer) at the collection site or at dedicated laboratory facility close (next door).

If frozen or same-day fresh left-over specimens will be used, specimen type and collection/storage medium must be validated by FIND for evaluation with the specific molecular POC. Device manufacturer will be consulted to this purpose (Table 3). Where possible, to avoid tempering with the integrity of biobanks by continuous freezing and thawing, frozen specimens will be retrieved from the freezers once and batch tested.

**Table 3.** Specimen types and volumes required for molecular POC devices

Type of specimen	Specimen type required for POC test			Volume of specimen required per test		
	DnaNudge	Mirai	GenomEra	DnaNudge	Mirai	GenomEra

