Frozen specimen (from biobank)	Specimen in UTM/VTM	Specimen in UTM/VTM	Specimen in Copan eNAT	Pipette 200-250ul VTM/UTM to swab chamber.	Mix 200 ul of a UTM with sample and add 800ul of the GenPad SSB	50ul of specimen collected in Copan eNAT
Same-day fresh specimen (left-over from diagnostic laboratory)	Nasal swab	Nasopharyngeal swab	Nasal swab	200-250ul VTM/UTM	200ul	50ul

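### Section 4.3 says spectrum bias is avoided for frozen and left-over specimens, but its selection rule does not assure this, and the primary accuracy estimate could depend on the mix of specimen sources

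*Protocol*

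**What the plan says.** For the prospective series, section 4.3 (Participant/specimen selection) gives the reason why the spectrum should be right: "Spectrum bias will be avoided by enrolling a consecutive series of study participants, and by using a prospective study design". It then makes the same promise for supplementary material: "If frozen or same-day fresh left-over specimens will be used, spectrum bias will be avoided by" two rules. Frozen specimens are obtained by "Randomly selecting specimens from biobanks, considering only inclusion criteria and previous RT-PCR qualitative result (positive or negative". Fresh left-overs are obtained by "Testing consecutive fresh left-over specimens from the diagnostic laboratory, considering only the inclusion criteria".

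Section 6 states a wider requirement: "All screening evaluations must be completed and reviewed to confirm that potential participants/specimens meet eligibility criteria". The exclusion criteria in section 3.6 include oxygen therapy and haemodynamic instability.

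On the role of these specimens, section 3.1 says: "Supplemental procedures will allow to achieve the primary objective of the study". Section 3.2 describes them as added to the prospectively collected specimens. The synopsis sets one target of 100 PCR-positive and 100 PCR-negative specimens, and section 3.3 ends the study when the required numbers are reached, with no count by source. Section 8.3 plans one analysis of Endpoint 1.1 in the per-protocol (PP) population. Its strata for Endpoint 2.1 are sex, days since onset, Ct, vaccination, previous infection and variant.

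On specimen type, section 6.1 bases diagnosis on "RT-PCR results performed on the routine diagnostic sample (nasopharyngeal swab"), whereas the Table 3 row "Same-day fresh specimen (left-over from diagnostic laboratory") lists a nasal swab for Nudge and GenomEra.

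**The concern.** The protocol's own argument against spectrum bias rests on consecutive, prospective enrolment. A biobank draw is neither, yet the assurance is repeated without qualification. Nothing in the document describes the biobanks' Ct or symptom-onset distribution, so the claim cannot be checked.

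Sensitivity of a molecular test depends on viral load. If banked positives have a different load, or come from patients whom section 3.6 would exclude, the estimate for the mixed set is not the accuracy in the symptomatic adults named in the primary objective. Because each device is evaluated in a different country, a different share of supplementary specimens per site could also make devices look different for reasons unrelated to the device.

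**Working it through.** **1. Eligibility wording.** Both rules in section 4.3 name the inclusion criteria only. Section 6 refers to eligibility criteria for participants and specimens alike. Of the four exclusions in section 3.6, oxygen therapy and haemodynamic instability bear on severity and so on spectrum. Nose bleeds and same-day co-enrolment mainly concern the act of swabbing.

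**2. Does selection by PCR result bias the estimate?** Sensitivity is the proportion index-positive among PCR positives. A random draw within PCR positives leaves it unchanged for the population that the biobank represents, and the same holds for specificity among PCR negatives. Fixing the ratio of positives to negatives distorts only predictive values, which are not endpoints. What matters is which population the biobank represents.

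**3. Test conditions by source** (section 6.1, Tables 2 and 3).

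| Device | Prospective specimen | Frozen specimen |
|---|---|---|
| Nudge | Nasal swab | 200-250 µl VTM/UTM pipetted to the swab chamber |
| GenomEra | Nasal swab | 50 µl of a specimen in Copan eNAT |
| Mirai | Nasopharyngeal swab (may be the reference sample) | 200 µl UTM plus 800 µl buffer |

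For Nudge and GenomEra a separate fresh nasal swab and a frozen tube specimen are different test conditions. This adds to dependence on the mix, but it is not spectrum bias.

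**4. Effect of the mix.** The protocol gives no figure for the mix effect that could be reproduced. With w the banked share of the positives:

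pooled sensitivity = w × Se(banked) + (1 − w) × Se(prospective)

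Se(prospective) = 97% is the lowest value in section 8.1. Both w and Se(banked) are assumptions; the protocol gives neither.

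| Assumed Se(banked) | w = 25% | w = 50% | w = 75% |
|---|---|---|---|
| 99% | 97.5% | 98.0% | 98.5% |
| 97% | 97.0% | 97.0% | 97.0% |
| 93% | 96.0% | 95.0% | 94.0% |
| 90% | 95.3% | 93.5% | 91.8% |

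Example: 0.5 × 0.93 + 0.5 × 0.97 = 0.950.

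**5. Coverage.** The Wilson 95% interval with 100 positives covers 97% with probability 96.9% when none are banked (exact binomial). With 50 banked (convolution of two binomials), coverage of the prospective value is 99.6%, 77% and 52% for banked sensitivities of 99%, 93% and 90%. In the first case coverage stays high, but the estimate is still shifted up by 1 point.

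**6. Spectrum alone, in either direction.** Assume sensitivities of 100%, 100%, 98% and 80% in the four Ct bands of section 8.3, lowest Ct first, and assumed Ct mixes:

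- prospective 15/40/33/12%: 0.15 + 0.40 + 0.33 × 0.98 + 0.12 × 0.80 = 96.9%
- high-load biobank 30/50/18/2%: 0.30 + 0.50 + 0.18 × 0.98 + 0.02 × 0.80 = 99.2%
- low-load biobank 8/27/40/25%: 0.08 + 0.27 + 0.40 × 0.98 + 0.25 × 0.80 = 94.2%

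**7. Are these specimens in the primary analysis set?** Section 3.5 admits specimens from people who consented to future research use. Table 4 in section 8.2 builds both populations from subjects enrolled with a signed ICF. Read literally, that could leave banked specimens out of PP, which does not fit the purpose given in section 3.1.

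**The case against.** Several points on the other side are sound.

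- A reader might call the biobank rule case-control sampling and infer that it inflates accuracy. The documents do not support that. Positives and negatives must both come from symptomatic adults with suspected COVID-19, draws are random within PCR result, and the rule leaves no room for picking by Ct.
- A reader might infer that the sources will be pooled with no breakdown. Nothing says so in words. It is the natural reading of sections 3.1, 3.2, 3.3 and 8.3 together, but Table 4 leaves it open, and section 8.3 defers subgroup definitions and data inclusion to a separate SAP, which may report by source.
- A reader might infer a known upward bias of several points. Assuming 90% prospective and 98% banked sensitivity, an 80/20 mix gives 91.6% and a 20/80 mix 96.4%. Those inputs have no basis in the protocol, and freezing or low viral load could push the other way.
- Sections 3.5 and 3.6 apply the inclusion criteria to participants or specimens and the exclusion criteria to participants only, so section 4.3 has a precedent. That narrows the conflict with section 6 but does not remove it.
- Safeguards exist. Supplementing is conditional on go/no-go criteria. Section 6.1 requires validation of specimen type and medium. Left-overs are taken consecutively. Ct and days since onset are to be described. However, section 3.1 concedes that data for the subgroup analyses may be lacking when supplementing is used.

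What stands is that the assurance is stronger than the rule behind it, that sections 4.3 and 6 differ, that the PP status of these specimens is unclear, and that Table 3 and the routine swab do not match. An SAP breakdown by source would not correct that protocol text.

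**Conclusion.** The point holds in a limited form. Avoidance of spectrum bias is not assured for supplementary specimens; it has not been shown that bias will occur. Random selection guards against hand-picking but transfers the biobank's spectrum to the study. For left-overs, consecutive sampling is a real protection, and the open issues are the missing exclusion criteria and the swab type.

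At w = 50%, the assumed banked sensitivities of 99% to 90% move the estimate from 1 point above to 3.5 points below the 97% prospective value. The effect is zero if the sources perform alike. The point arises only if supplementing is used and the specimens enter the primary analysis. Within those limits, a pooled figure without its source breakdown could not be read as accuracy in consecutive symptomatic patients.

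**What to change.** - **Section 4.3:** say that random or consecutive selection limits spectrum bias. Apply the exclusion criteria to banked and left-over specimens where the data exist, in agreement with section 6. Compare Ct and days since onset by source where available.
- **Section 8.2:** state whether banked and left-over specimens enter the PP population, and adapt the Table 4 definitions to match.
- **Section 8.3:** report Endpoint 1.1 by source (prospective, fresh left-over, frozen) beside any pooled figure. Which estimate leads is the sponsor's choice, provided it is fixed in advance.
- **Section 6.1:** reconcile the nasal-swab left-overs in Table 3 with the nasopharyngeal routine specimen.

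The work is wording and one table. The cost is precision: 97/100 gives a Wilson 95% interval of 91.5% to 99.0%, 48/50 gives 86.5% to 98.9%, and 24/25 gives 80.5% to 99.3%. This is why a prospective-only headline should not be imposed: with only 20 prospective positives, 19/20 gives about 76% to 99%. Some banked specimens without clinical data may also become unusable.

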### **Index test**

There will be no risk of index test results review bias as result interpretation is performed directly by the device and the personnel operating the device will only need to record the results as they are.

To avoid the risk of sample degradation and to comply with the intended use of the device as POC, the operator will run the test within maximum 3 hours after sample collection or as per instructions agreed with the specific device manufacturer.

Ideally, the molecular POC device will be placed in the same room where specimen collection takes place; in case this will not be possible, the device will be placed in dedicated laboratory facilities close (next door) to participants recruitment/sampling location.

Should the test fail, no repetition will be performed. The result will be recorded as reported by the device (e.g., failed, invalid). This will prevent that molecular POC devices allowing test repetition from left-over material without the need of collecting a new specimen may be favoured compared to POC requiring a new specimen for test repetition, like Nudge test.

Standardization of device operation by different users, part of the study team, will be ensured with proper training at the beginning of the study. Proficiency and/or competency assessments will be conducted before initiating and/or during the study at discretion of FIND study team. (SITE-specific

procedures may be added.) As part of the training, molecular POC operators will be instructed to perform the test after all relevant samples will be collected and the study participant will have left the sample collection/testing area. Additionally, the molecular POC testing will be done in the absence of the treating clinician to avoid that the results of the molecular POC are mistakenly used or influence the clinical decision-making process.

